# 6.8 Randomization and Blinding of Study Drug

This section is not necessary as this study is not a randomized or blinded trial.

# 6.9 Receiving, Storage, Dispensing and Return or Disposal of Study Agent

**Table 2:** Study Agent information at a glance:

Name	Source	Storage	Dispensing	Disposal
Metformin 850 mg	Drogueria Americana	CHW	CHWs	NA
tab	-	headquarters		
Glibenclamide 5	NeoEthicals	""	""	NA
mg tab				
Aspirin 81 mg tab	Drogueria Americana or	""	""	NA
	NeoEthicals			

### 6.9.1 Receipt of Drug Supplies

Metformin, glibenclamide, and aspirin will be obtained from Drogueria Americana and NeoEthicals, S.A., two reputable pharmaceutical distributors operating in Guatemala City with whom SLM has worked for some time.

An inventory will be performed and a drug receipt log filled out and signed by the person accepting the shipment. The designated study staff will count and verify that the shipment contains all the items noted in the shipment inventory.

Version #: 1.0

[name]

## 6.9.2 Storage

Storage of medications will occur in a storage locker in the CHWs' headquarters in Quixaya. As such, they will not be exposed to sunlight or extremes of temperature. In the temperate climate of highland Guatemala, temperatures will not routinely vary from the 68-77 degree F storage temperature range and excursions would not exceed the 59 to 86 degrees F recommended for these medications

# 6.9.3 Dispensing

Medications will be dispensed to each patient at monthly visits by CHWs as guided by the diabetes smartphone application. Adherence to medication will be assessed at each monthly visit by standardized patient report (see Appendix 3 for more information on how adherence assessment).

### 6.9.4 Return or Disposal

Unused medication at the end of the study will remain with the SLM CHW program to be used by patients continuing in SLM's diabetes treatment program.

# 7 Study Procedures

# 7.1LABS

All patients will have POC HbA1c testing performed at baseline and every 3 months. The ADA does recommend individualization of A1c testing, advising quarterly checks in patients not meeting glycemic goals and at least twice yearly in those meeting treatment goals. While we do intend to implement individualized testing in the diabetes program after the study period, testing will be every 3 months for all patients during the study period to allow for more uniform evaluation of program efficacy at the predetermined times of endpoint analysis (6 and 12 months for primary endpoints).

A1c testing will be performed with A1CNow®+ (PTS Diagnostics) POC capillary blood analyzers. This analyzer has been granted a CLIA waiver and has been certified by the National Glycohemoglobin Standardization Program (NGSP).

Capillary blood glucose measurements will be conducted at baseline and monthly using the Bayer Contour® POC system. This is also CLIA-waived and has been validated in comparisons with plasma/serum glucose analyzers.

Both aforementioned POC testing systems are designed to be used by laypeople and patients without medical training, making them very appropriate for use by frontline health workers, as in our study.

Testing of serum creatinine will be checked at baseline for all patients with prior history of chronic kidney disease prior to administration of metformin or glibenclamide. Baseline creatinine will also be strongly recommended for patients with hypertension (defined as either taking antihypertensives or baseline BP  $\geq$ 140/90) and/or duration since diagnosis of diabetes of 10 years or more. Serum creatinine will be checked at SLMH and reviewed by the medical director, who will then determine patient eligibility for metformin and/or glibenclamide therapy based on calculated eGFR.

Ideally, serum creatinine would be tested in all patients at baseline and prior to administration of metformin and glibenclamide. However, this is not performed routinely for diabetic patients in the San Lucas area due to the expense and availability of travel. Requiring testing for all patients prior to administration would likely severely restrict participation as it is likely many patients would not travel to San Lucas to have necessary testing done and subsequently be lost to follow up. For this reason, we have adopted a risk-factor based targeted testing strategy for checking renal function.

Version #: 1.0

[name]

## 7.2 Established Standard of Care:

The current standard of care in the rural communities around San Lucas Tolimán is not consistent. There is a clinic based at SLMH in San Lucas Tolimán, which sees a group of ~100 patients, usually on a monthly basis. These patients are by and large from the city itself, as it is very difficult for patients from the rural communities to spare the time and expense to travel to San Lucas. This clinic is run by the two supervisors of the CHW program, who have significant experience in working with patients with diabetes and can titrate metformin and glibenclamide if blood glucose is persistently elevated. SLMH CHWs also hold clinics 3 of the 19 rural communities. However, supplies of medications and testing supplies are inconsistent and thus patients are administered medications based more on which medication and dosage is available rather than based on clinical judgement and patient condition. The CHWs staffing these rural clinics are unable to titrate diabetes medications in response to persistent hyperglycemia or adverse effects. Services at all of these clinics are limited to measurement of vital signs, blood glucose (when supplies available), dispensing of metformin and glibenclamide, counseling on diet and lifestyle, and referral to SLMH medical director [name] if complications are suspected based on CHW clinical judgement. No further laboratory testing or other assessment is routinely performed.

# 7.3 Study Visits

# 7.4.1 Screening/Baseline:

### Training of CHWs

While not an element of direct patient care, an essential part of the diabetes program will be the training of CHWs prior to enrollment of patients. CHWs undergo a 6 week training program emphasizing health education and identification of patients who require definitive medical care. Many also have experience in using a mobile application to track and treat children with chronic malnutrition. However, many lack specific training on the management and complications of diabetes. We have designed training to fill in these gaps in diabetes-specific knowledge and to teach CHWs how to use the smartphone application and POC testing devices. We will also instruct CHWs on human subjects research ethics and the process of obtaining informed consent, as they will act as collaborating investigators.

Training will consist of the following elements (allotted times are approximate):

- Didactic sessions focusing on the basics of diabetes pathophysiology, lifestyle and medication management, and complications - 8 hours total. The PowerPoint presentation that will used for these session has been uploaded to ARROW in the Supplemental Information section.
- Didactic session on human subjects research protections and informed consent 2 hours. We will use
  adapted CITI training that was developed by researchers from Marywood University on a prior research
  project performed with the SLM CHWs. These researchers have given us permission to use these
  materials, which are available in English and Spanish. As many of the CHWs have already reviewed this
  material, the reuse of this resource will have the added benefit of reinforcing their prior learning. The
  training documents are uploaded in the ARROW application.
- Practical workshop on the use of POC testing devices (A1CNow®+ and Contour® devices), measurement of blood pressure and pulse using the ReliOn™ BP200 automatic blood pressure cuff, body temperature using a digital thermometer, and anthropometric measurements (weight, height, waist circumference) 4 hours
- Hands-on practice with the application with trainers taking on the role of patients to simulate patient encounters 8 hours

Training will be conducted by study investigators with the assistance of CHW program coordinators, who have already gone through such training in order to carry out beta testing of the application with a small group of patients. We anticipate training approximately 30 CHWs for the diabetes program. As the program matures, the CHW coordinators will gradually take over more responsibility for CHW training to ensure local ownership and sustainability of the program (a "train the trainers" model).

Version #: 1.0

[name]

For the first several months after completion of the training program, CHWs will be paired with one of the CHW coordinators while seeing patients for continued clinical mentorship and guidance.

### Enrollment Visit

0

Patients will be screened for study eligibility on the same day of potential enrollment. If they are eligible, informed consent will be obtained and the CHW will proceed with enrollment and initial treatment of the patient with the guidance of the enrollment module of the smartphone application. The enrollment visit will consist of the following elements:

- Screening questions (Appendix 1) Determine if patient is eligible to participate in the study. Done with verbal consent. If eligible, written and verbal consent obtained for full study participation and CHW proceeds to the next step.
- Collection of demographic information and relevant past medical history (Appendix 1) This information facilitates the creation of a patient database and clinical registry, determines the patient's glycemic goal and if they need renal function testing prior to initiation of medications, and informs a decision about chronic aspirin therapy for secondary ASCVD prevention (Appendix 2). Glycemic goals are generally consistent with ADA guidelines and are determined as follows:
  - Patients <65 years old with <2 comorbidities (CAD, CVD, COPD, CKD, cancer)
    - A1c goal ≤7%
    - FBG 80-130 mg/dL
    - PPBG <180 mg/dL

    - Patients ≥65 years old or <65 years old and with ≥2 comorbidities (as listed above)
      - A1c goal ≤8%
      - FBG 90-150
      - PPBG <200 mg/dL

- Medication history, adherence and side effects (Appendix 3) This information factors into the confirmation of diabetes with A1c testing (for example, if a patient is not taking any medications and their A1c is 5.2, they may not have diabetes) and provides information for the application to determine starting medication for each patient. Information about whether a patient is taking medication for hypertension will also factor into whether renal function testing is recommended prior to initiating medication treatment.
- Glycemic testing, vital signs, and other anthropometric data Fasting status, defined as no caloric intake for the past 8 hours, is determined. Blood glucose and hemoglobin A1c are collected for each patient. If hypoglycemia or severe hyperglycemia are identified at this stage, the application initiates management protocols (Appendix 4 and Appendix 5). CHWs also measure blood pressure, pulse (also collected by the automatic BP cuff), height, weight, and waist circumference. Hypotension or hypertension are addressed according to the protocol described in Appendix 12
- Screening for possible complications of diabetes (Appendix 6) The application guides CHWs through an
  assessment for possible complications of diabetes, including diabetic foot ulcers, angina, and diabetic eye
  disease.
- Recommendations for referrals (Appendix 7) Based on information collected and entered by the CHW, the application will make recommendations regarding the need for a referral to SLMH and evaluation the medical director [name]. Referral recommendations are classified as emergent (recommended immediate transport), urgent (evaluation by physician within 1-2 days), or routine (evaluation by physician within 1-2 weeks). CHWs are prompted by the application to immediately arrange for referral and transport for emergent conditions (e.g. current chest pain suspicious for angina) as soon as these conditions are identified. The recommendation for referral in these cases is a "hard stop" and the CHW will not be able to proceed with application questions until the emergent situation is addressed and

Version #: 1.0

[name]

definitive care arranged. These recommendations for referrals are consistent with the WHO protocol for diabetes management in low-resource settings  $^{\rm 47}$ 

Medication recommendations and counseling - Based on medication history, A1c, and glycemic goal, the
application uses an algorithm to determine a recommended medication regimen for the patient, including
the amount of medication to dispense (Appendix 8). The application provides information on how to take
the medication and how to avoid adverse effects, which the CHW discusses with the patient (Appendix 9).
The CHW then uses the "teach-back" method to ensure that the patient understands how to take their
medication. The CHW will also provide patient education on diabetes self-management, including diet,
physical activity, and foot care, with the assistance of demonstration materials developed for the program
(uploaded to ARROW application in the Supplemental Information section).

### Physician Oversight

Within 1-2 days of the enrollment visit and every subsequent visit, patient data from the smartphone application will be uploaded to a secure online database viewable to the supervising physician, [name]. Within 1 week of each visit, [name] will review the visit summary for each patient and either approve the current treatment or recommend changes to the treatment, including changes to the patient's glycemic target as necessary. Also during that 1 week timeframe, any changes recommended by [name] will be communicated to the patient through the health promoter coordinators and/or the health promoter who saw the patient.

If CHWs have questions regarding patient care while conducting a patient visit, they will contact one of the CHW coordinators and or [name] via telephone for advice on how to proceed.

#### 7.4.2 Follow up:

Acceptable Window for Study Visits (including weekends)

Visit	Window	Activities
Monthly follow up visits	+/- 1 week	Assessment of the following:         Outright Medication adherence and tolerance         Glycemic control with blood glucose         Oresence of diabetes complications         Refill of medications, with titration of dosage as needed         Diabetic education
Month 3 visit	+/- 1 week	Same as for monthly visit with the exception that A1c is checked (if indicated) in addition to blood glucose and is used for medication titration

### Monthly Visits

CHWs will meet with patients once per month to follow up on adherence and tolerance to medications, assess glycemic control, assess for complications of diabetes, refill medications (with dosing adjustments as needed for side effects, non-adherence or poor glycemic control), and provide diabetic education. These monthly visits will be facilitated by the smartphone application monthly protocol. This protocol mirrors the enrollment protocol as described above, with the following exceptions:

- Basic demographic information and medical history are not reassessed. This information is carried forward from the enrollment visit
- Blood glucose alone is collected. A1c is not collected unless it was recommended to be done the month
  prior and was not collected at that time
- Algorithms for medication adjustments are based on blood glucose, preferencing fasting glucose over postprandial glucose (Appendix 10)

### Month 3 Visit

Version #: 1.0

[name]

At every 3rd monthly visit, starting with the visit 3 months after enrollment, A1c will be assessed. When A1c is checked, the month 3 medication titration algorithm (Appendix 11), is used rather than the monthly titration algorithm, which uses blood glucose. This protocol also considers the current glucose measurement to account for cases in which glycemic control may have improved significantly in the past month due to medication or lifestyle changes, but A1c may still be above goal due to earlier hyperglycemia. For example, if a patient with A1c goal of 7 has an A1c of 7.5, but FBG of 105, the application will recommend that the patient continues with the current medication dosing rather than recommending a dose increase. Other than checking A1c and using the A1c-based algorithm as indicated, the procedures performed at the month 3 visit are identical to those of the monthly visit.

## 7.4.3 Unscheduled:

The CHWs live in the same communities as the patients they will be serving. As such, we recognize that patients may come to them with concerns outside of the structure of monthly visits as described above. We have designed an additional module for the smartphone application that guides the CHWs through an assessment for hypoglycemia or severe hyperglycemia and possible complications of diabetes. This module uses the same relevant protocols from the enrollment and monthly visits (see Appendix 4, Appendix 5, Appendix 6, Appendix 12). If a patient or CHW has a concern outside of the scope of these protocols, the CHW will contact a CHW coordinator and/or the medical director [name] for guidance.

### 7.4.4 Final Study Visit

All patients will be followed until at least 6 months post enrollment. Safety monitoring will occur on a continuous basis during the study and an interim analysis of efficacy will occur at the 6 month point. If permitted based on funding and personnel availability and the ability and desire of our local partners in Guatemala, patients will be continued to be followed out to 12 months post enrollment.

This study is based around the implementation of a program that the San Lucas Mission intends to continue indefinitely. Thus, patients who participated in this study will have the opportunity to continue their treatment through the CHW-led diabetes program. The study will inform a quality improvement process for this program and work to ensure program sustainability.

# 8 Study Analysis

### 8.1 Sample Size Determination

For this study, we plan to recruit approximately 150 patients based on the known population of diabetics in the rural communities surrounding San Lucas Tolimán. Of these, we hope to enroll at least 100 patients in the study. Using these numbers, statistical power was calculated using the UCSF online sample size calculators  for a one-group before-after study. The following parameters were used for calculation:

- a = 0.050
- β = 0.200
- SD for outcome = 2.4 (this was the reported pretreatment SD for A1c for a population of 174 indigenous diabetics upon enrollment in a diabetes treatment program in rural Guatemala)
- Within-subject A1c correlation coefficient (rwithin) of 0.928 (this is based on an analysis conducted to determine the accuracy and precision of the A1CNow®+ testing device49, which we are using in our study) Sample size = 100

With this sample size, we will have adequate power to detect an effect size as small as 0.257% A1c and should easily be able to detect more clinically significant differences of 1% A1c or more.

Version #: 1.0

[name]

Another primary outcome will be the proportion of patients meeting treatment goals vs this proportion at baseline. Using the above website, the same parameters for a and  $\beta$ , sample size of 100, and a baseline proportion of patients meeting treatment goals of 13% (this is based on a needs assessment that we conducted as part of this project), we would have 80% power to detect a proportion of 30.2% of patients with good glycemic control (OR 2.896 compared to baseline).

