## 8.2 Statistical Methods

The primary endpoints will be hemoglobin A1c at 6 months and 12 months post-enrollment. This will be analyzed and reported in two ways:

- Mean hemoglobin A1c in the study group compared to mean value at baseline
- Percentage of patients meeting treatment goal for hemoglobin A1c compared to this percentage at baseline. Treatment goal will be A1c ≤7 for most patients, A1c ≤8 for patients age 65 or older or who have 2 or more comorbidities, or other individualized goal for select patients as determined by the medical director ([name])

Secondary endpoints and analyses will include:

- Mean A1c and proportion of patients at goal at 3 months and 9 months.
- Mean FBG at 6 and 12 months compared to baseline value
- Mean BMI at 6 and 12 months compared to baseline
- Mean waist circumference at 6 and 12 months compared to baseline ٠
- Mean blood pressure at 6 and 12 months compared to baseline
- Number and percentage of patients identified as potentially having the following complications: Ischemic chest pain
  - 0
  - 0 Foot ulcers
  - Ophthalmologic complications 0
  - Hypertension 0
- Percentage of patients successfully completing referrals for potential complications
- Number and percentage of patients referred for poor glycemic control or intolerance of diabetic medications and percentage of these patients who complete referral
- Prevalence of adverse effects of metformin and hypoglycemia symptoms throughout the study
- Patient medication adherence throughout the study and at 6 and 12 months compared to baseline (proportion patient reporting each level of adherence)
- CHW compliance with medication recommendations provided by the application (proportion of visits)

Differences in continuous variables (e.g. mean A1c) will be analyzed using paired, 2-tailed t tests. Differences in categorical values (e.g. percentage of patients meeting treatment goal for A1c) will be analyzed using the McNemar test for binary matched-pairs data.

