## 8.3 Subject Population(s) for Analysis

There will be no randomization and there is only one group, so all patients enrolled will be analyzed to the extent of their participation. Analyses will be as described above in section 8.2. Planned subgroup analyses include patients with A1c less than or equal to treatment goal at baseline, patients above treatment goal at baseline, and patients with A1c ≥9 at baseline.

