### 9.2.2.1 Missing Data

The smartphone application will assist in ensuring complete data entry in that most fields are required before the CHW can proceed to the next section of the visit and most data is entered through the use of radio buttons, prepopulated list options, and parameter-limited text boxes. Retention and follow up of patients will be enhanced by visiting patients who miss monthly group visits at their homes. Only patients who completed follow up to each relevant time point (e.g. 6 months, 12 months) will be included in these analyses.

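### Does the 30.2% power figure for the proportion at A1c goal need replacing because it states no assumption about discordant pairs?

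*Combined protocol and SAP*

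**What the plan says.** Section 8.1 opens by saying that power was calculated "for a one-group before-after study". For mean A1c it lists alpha 0.05, beta 0.20, an SD of 2.4, a sample size of 100 and a "Within-subject A1c correlation coefficient (rwithin) of 0.928". Of that last value it says "this is based on an analysis conducted to determine the accuracy and precision" of the testing device.

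For the proportion at goal it keeps alpha, beta and the sample size of 100, adds a 13% baseline from the needs assessment, and concludes that "we would have 80% power to detect a proportion of 30.2% of patients with good glycemic control (OR 2.896 compared to baseline". It gives no correlation or discordant proportion for goal status, and names no formula.

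Under section 8.2, differences in categorical values "will be analyzed using the McNemar test for binary matched-pairs data". The version (exact, continuity-corrected or uncorrected) is not named.

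On who is analysed, section 8.3 says "There will be no randomization and there is only one group, so all patients enrolled will be analyzed to the extent of their participation". Section 9.2.2.1 says "Only patients who completed follow up to each relevant time point (e.g. 6 months, 12 months) will be included in these analyses", and plans to support retention by "visiting patients who miss monthly group visits at their homes". Section 8.1 makes no allowance for dropout.

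**The concern.** McNemar's test uses only patients who move into or out of goal between baseline and follow-up. Two studies with the same 13% and 30.2% can have quite different power, depending on how many patients move in each direction. A McNemar power statement without that input cannot be checked.

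Two further features suggest a slip. The 30.2% is what the standard continuity-corrected formula returns for two independent groups of 100 each, a design this study does not have. The one calculator page cited (reference 48) is for the paired t-test, so the source of the binary figure cannot be traced. Section 8.1 also credits mean A1c with a very high within-patient correlation, while the figure for goal status, a threshold on the same measurements, credits none.

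This is the only power statement for one of the two primary analyses. If it overstated power, the study could miss a real gain in the proportion at goal.

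**Working it through.** **Inputs from section 8.1.** p1 = 0.13, p2 = 0.302, n = 100, alpha = 0.05, power = 0.80. Two-sided testing is assumed; the protocol states it only for the t tests.

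**Odds ratio.** (0.302/0.698) / (0.13/0.87) = 2.8955, printed as 2.896.

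**Reproducing 30.2% with two independent groups.** With p̄ = (0.13 + 0.302)/2 = 0.216 and d = 0.172:

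- Uncorrected: n = [1.96·√(2·0.216·0.784) + 0.8416·√(0.13·0.87 + 0.302·0.698)]² / 0.172² = 88.7 per group.
- Continuity-corrected: n' = (n/4)·[1 + √(1 + 4/(n·d))]² = 99.96 per group.
- Solving the corrected formula for p2 at 100 per group gives 30.196%.

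**Reproducing 30.2% with McNemar.** Let p11 be the proportion at goal both times. At zero correlation:

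- p11 = 0.13 × 0.302 = 0.0393
- leaves goal: 0.13 − 0.0393 = 0.0907
- reaches goal: 0.302 − 0.0393 = 0.2627
- discordant: 0.0907 + 0.2627 = 0.3535 (from unrounded values)

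Power is found by enumerating the number of discordant pairs, binomial(100, 0.3535), and their split. It is 80.2% exact, 80.1% continuity-corrected and 85.0% uncorrected. The proportion detectable at 80% power is 30.16% exact and 30.18% continuity-corrected.

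Three calculations therefore give 30.2% after rounding. The odds ratio does not separate them, because 2.896 is what any of them gives once the proportion is rounded to 0.302.

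**Effect of pairing, 100 completers.** The documents give no correlation for goal status, so the values below are assumptions, read as the correlation of an underlying bivariate-normal A1c.

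| Assumed latent r | Discordant | Exact power | Uncorrected power |
|---|---|---|---|
| 0 | 35.3% | 80.2% | 85.0% |
| 0.3 | 30.5% | 86.3% | 90.8% |
| 0.5 | 26.9% | 91.4% | 94.7% |
| 0.7 | 22.7% | 96.5% | 98.1% |
| 0.928 | 17.7% | 99.9% | 99.96% |

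Without any such model, non-negative association limits discordance to between 0.172 (nobody leaves goal) and 0.3535. Exact power then lies between 99.98% and 80.2%.

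**Fewer completers (illustrative; no dropout rate is given).**

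| Completers | Exact, r = 0 | Exact, r = 0.3 | Uncorrected, r = 0 |
|---|---|---|---|
| 99 | 79.7% | 86.0% | 84.6% |
| 90 | 75.0% | 82.0% | 81.3% |
| 80 | 69.0% | 76.7% | 76.9% |

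At r = 0 the exact test needs all 100 completers for 80%; the uncorrected test needs 87. At 80 completers, the exact test reaches 80% from r of about 0.40.

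**The case for a change.** The best case for a change is that two unstated inputs pull in opposite directions. Ignoring pairing understates power, and having no completer allowance overstates it. Section 8.1 only hopes for at least 100 enrolled, the needs assessment counted 119 diagnosed patients in the rural communities, and a paired test can use only patients measured at both times. With the exact test and zero correlation, any loss below 100 takes power under 80%, to 75.0% at 90 completers. One or two sentences would let a reader see this.

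The arithmetic stands, and such sentences would be welcome. But the shortfall needs three conditions together: the exact or continuity-corrected test, fewer than 100 completers, and almost no association between a patient's goal status at baseline and at follow-up. The last is unlikely for repeated A1c in the same person. With r = 0.3 the exact test still has 82.0% at 90 completers, and the uncorrected test has 81.3% there even at r = 0. Losing 20 patients would be more serious, but that is a retention matter which rewording the power statement would not cure.

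The contrast with 0.928 carries less weight than it first appears to. That value is for continuous A1c and comes from a device evaluation. For goal status at 13% and 30.2%, the correlation between the two yes/no values cannot exceed 0.0907/√(0.13·0.87·0.302·0.698) = 0.59. Silence about correlation is also not an assumption that it is zero. Whether 0.928 suits the mean-A1c calculation is a separate question.

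**Conclusion.** The concern does not call for a change. Section 8.1 does omit the discordant proportion, the McNemar version and the expected number of completers, and the origin of 30.2% cannot be established. The figure is nevertheless correct for exact or continuity-corrected McNemar with 100 pairs at zero correlation, and conservative at any positive correlation: exact power is 86% to 99.9% for assumed latent r from 0.3 to 0.928. It matches an independent-groups result only because that result is also an answer with no benefit from pairing.

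Nor does anything downstream depend on it. This is a single-group feasibility study whose recruitment number comes from the known diabetic population, so a restated power figure would leave enrolment, the planned test and the conclusions as they are. The conclusion assumes two-sided testing, non-negative association between baseline and follow-up goal status, and close to 100 completers. If completers fell to around 80 and association were weak, power would be about 69% to 77% with the exact test.
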